## SELECTION CRITERIA

### Inclusion Criteria:

- Patients with prediabetes, defined for the existence impaired glucose tolerance (glucose between 140 and 199 mg/dL at the 2 hours of the Oral Tolerance Glucose Test (OGTT) with impaired fasting glucose (fasting glucose between 100 and 125 mg/dL)
- Patients who accept to participate in the study and sign the informed consent letter.

### Exclusion Criteria:

- Patients with diagnosed Type 2 Diabetes previously or detected during the OGTT
- Patients in actual treatment or during the last 3 months with metformin, pioglitazone or another antidiabetic drug, including insulin
- Serum creatinine > 1.6 mg/dL
- Hypertriglyceridemia very high (>500 mg/dL)
- Pregnant women
- Altered arterial hypertension (Systolic >180 mmHg or Diastolic >105 mmHg)
- Excessive alcohol intake, acute or chronic
- Medications or medical conditions that affect glucose homeostasis (thiazides, beta blockers, glucocorticoids for systemic use, weight-reducing drugs or anorexigenics, Cushing's syndrome, thyrotoxicosis)

## **VARIABLES**

### **INDEPENDENT VARIABLE**

#### **1) Intervention**

a. Measurement level: Qualitative nominal

b. Indicator:

1. A for the group receiving quadruple therapy (linagliptin + empagliflozin + metformin + lifestyle modifications)
2. B for the group receiving standard therapy (metformin + lifestyle modifications)

c. Conceptual definition: Therapeutic strategy whose purpose is to avoid alterations in glucose metabolism and progression to DM2, and reduce cardiovascular risk.

d. Operational Definition:

1. When patients receive 1 tablet of linagliptin 2.5mg / metformin 850mg every 24 hours + 1 tablet of empagliflozin 12.5mg / metformin 850mg every 24 hours + lifestyle modifications for 12 months
2. When patients receive 1 tablet every 12 hours of metformin 850 mg + lifestyle modifications for 12 months

### **DEPENDENT VARIABLES**

### **1) Improvement in glucose metabolism (regression of hyperglycemia and glucose intolerance)**

- a. Type of variable and level of measurement: Qualitative dichotomous nominal
- b. Indicator: Yes or No
- c. Conceptual definition: The ability of therapeutic interventions to reverse fasting hyperglycemia and glucose intolerance.
- d. Operational definition: It will be considered as YES when the fasting glucose level at 12 months after the start of the intervention is <100mg / dl and the glucose at 2h during the OGTT is <140mg / dl, and as NO when at 12 months after the start of the intervention, fasting glucose levels are  $\geq 100$ mg / dl and / or at 2h during OGTT are  $\geq 140$ mg / dl.

### **2) Glycosylated hemoglobin**

- a. Type of variable and level of measurement: Quantitative ratio
- b. Indicator: %
- c. Conceptual definition: Biochemical test indicating the degree of glycemic control during the last 3 months
- d. Operational definition: Glycosylated hemoglobin values measured at the beginning and end of the study by HPLC technique.

### **3) Pancreatic beta cell function (Insulin Oral Disposition Index = IDOI)**

- a. Type of variable and level of measurement: Dependent, Quantitative of reason
- b. Indicator: pmol / mmol
- c. Conceptual definition: Pancreatic beta cell's ability to secrete enough insulin and maintain normal glucose levels
- d. Operational definition: Value obtained with glucose and insulin values during the OGTT by applying the following formula:  $(\Delta I_{0-30}) / (\Delta G_{0-30})$ , where  $(\Delta I_{0-30})$  = difference in the value of insulin measured at 0 and 30 minutes of the OGTT; and  $(\Delta G_{0-30})$  = difference in the glucose value measured at 0 and 30 minutes of the OGTT, which will be measured at the beginning and at the end of the intervention in each study group.

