Several pathophysiological mechanisms have been described in insulin resistance. At the liver level it has been observed that there is a decrease in the number and activity of insulin receptors, decrease in glucose uptake due to a decrease in the number and activity of glucotransporters and, by the condition of some enzymes in the glycolytic pathway that secondaryly prevent the ingress of glucose, as well as an effect of free fatty acids at this level interfering with insulin signaling. On the other hand, at the muscle level this insulin resistance is also very important, because this is the place where the greatest uptake of insulin-dependent glucose (80%). Here there has also been a decrease in glucotransporters (in this case GLUT4), accumulation of triglycerides and excess free fatty acids that compete with glucose as an energy substrate and increase malonilCoA levels that have the ability to inhibit carnitinepalmitotransferase type 1, an important enzyme for beta oxidation of fatty acids. In addition, both at the liver, muscle and mainly adipose level, an interesting interrelationship has been found between different cytokines, such as tumor necrosis factor alpha (TNFa) that conditions insulin resistance by causing phosphorylation of intracellular part of the insulin receptor and insulin receptor substrate 1 (IRS-1), and its counterpart, the adiponectin which is the only cytokine protective against insulin resistance.

Due to this insulin resistance, at the peripheral level the glucose (muscular) uptake decreases and at the hepatic level it is not able to suppress glucose production, therefore, as a compensatory mechanism the beta cell increases insulin secretion and thanksAt this hyperinsulinemia, equilibrium is achieved and euglycemia is maintained, so hyperinsulinemia is an indirect marker of insulin resistance [11].

However, over time and the persistence of insulin resistance and the increase of some toxic factors for the beta cell (glucose and lipids), it begins to deplete and decrease insulin secretion, so that ability to maintain suppressed hepatic glucose production and fasting hyperglycemia appears (Figure 1), until we reach diagnostic levels of DM2 where we have a 50-80% reduction in the functional capacity and volume of beta cells [11, 14].

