#### 4) Pancreatic beta cell function

- a. Type of variable and level of measurement: Dependent, Quantitative of reason
- b. Indicator: pmol / mmol
- c. Conceptual definition: Pancreatic beta cell's ability to secrete enough insulin and maintain normal glucose levels
- d. Operational definition: This will be obtained using the OGTT glucose and insulin values by applying the following formula:  $(\text{IncAUCG0-120}) / (\text{IncAUCI0-120})$ , where  $(\text{IncAUCG0-120})$  = increase in the area under the curve of glucose during the 120 minutes of the OGTT obtained by the trapezoidal rule, and  $(\text{IncAUCI0-120})$  = increase of the area under the insulin curve during the 120 minutes of the OGTT obtained by the trapezoidal rule.

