#### 5) Insulin Sensitivity (Matsuda Index)

- a. Type of variable and level of measurement: Dependent, Quantitative of reason
- b. Indicator: natural numbers
- c. Conceptual definition: The ability of insulin to promote glucose uptake by muscle tissue, to suppress glucose production by the liver and to prevent lipolysis in adipose tissue.
- d. Operational definition: It will be evaluated using the Matsuda index with glucose and insulin values during the OGTT using the following formula:

$$\text{Insulin sensitivity} = \frac{10000}{\sqrt{(G_0 \times I_0) \times (G_{0-120} \times I_{0-120})}}$$

Where  $G_0$  = basal glucose

$I_0$  = basal insulin

$G_{0-120}$  = average glucose during OGTT

$I_{0-120}$  = average insulin during OGTT

This measurement will be carried out at the beginning and at the end of the intervention in each of the study groups.

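### The variable named a disposition index is early insulin secretion with no insulin-sensitivity term, so it can understate islet function, or move against it, in the arm whose sensitivity improves more

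*Combined protocol and SAP*

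**What the plan says.** Variable 3 under Dependent Variables is headed "Pancreatic beta cell function (Insulin Oral Disposition Index = IDOI". Its conceptual definition is the beta cell's capacity to secrete enough insulin to keep glucose normal. Its operational definition has two terms:

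- Numerator: "difference in the value of insulin measured at 0 and 30 minutes of the OGTT".
- Denominator: "difference in the glucose value measured at 0 and 30 minutes of the OGTT".

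The unit line, "Indicator: pmol / mmol", agrees with that formula: insulin over glucose and nothing else.

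Insulin sensitivity is a separate item, variable 5: "It will be evaluated using the Matsuda index with glucose and insulin values during the OGTT using the following formula". It is never multiplied into variable 3.

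The other beta-cell measures are:

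- Variable 4, a ratio of incremental areas for glucose and insulin (its insulin term is "increase of the area under the insulin curve during the 120 minutes of the OGTT obtained by the trapezoidal rule"). It has no sensitivity term.
- HOMA-B, under Laboratory procedures and techniques. It has no sensitivity term.
- An insulin availability index during the OGTT, in the same list. No formula is given.
- A hyperglycemic clamp under Mid-term evaluation, at 6 months. It is not listed at baseline or 12 months, and no index is derived from it.

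The Statistic Analysis section plans unadjusted group comparisons and an analysis of deltas.

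**The concern.** A disposition index judges secretion against the demand that insulin resistance creates. The name and the word enough in the conceptual definition both point to that idea, but the formula has no term for demand. The protocol's own pathophysiology section shows why this matters. Faced with resistance, "as a compensatory mechanism the beta cell increases insulin secretion", and the same paragraph treats high insulin as an indirect marker of resistance. A high ratio can therefore reflect high resistance rather than good islet function.

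The hypothesis claims that quadruple therapy does better on islet function and on insulin resistance. With the written formula, success on resistance tends to push down the measure of islet function. A real islet benefit could then look smaller than it is, or look like a loss. Islet function is one of the three outcomes named in the research question, the goal and the hypothesis, so a mislabelled index affects a headline conclusion.

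**Working it through.** The plan gives no numerical value for this index, so there is no figure to reproduce. The sample size does not depend on it. The check is algebra plus one illustration.

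**1. Identity.** Let S = ΔI(0–30)/ΔG(0–30), the index as written. Let M = the Matsuda index and D = S × M, the sensitivity-adjusted index. Then S = D/M. Comparing arm A with arm B:

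S_A/S_B = (D_A/D_B) ÷ (M_A/M_B)

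On the ratio scale, a sensitivity gain shared by both arms cancels. Only the difference between arms matters.

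**2. Equal adjusted function (D_A/D_B = 1).** The sensitivity advantages below are assumptions, because the documents give none.

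| M_A/M_B | S_A/S_B | Written index, A relative to B |
|---|---|---|
| 1.10 | 1/1.10 = 0.91 | −9% |
| 1.20 | 1/1.20 = 0.83 | −17% |
| 1.30 | 1/1.30 = 0.77 | −23% |

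Put the other way, an arm with 20% more sensitivity needs an adjusted index 20% better just to tie on the written one.

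**3. Illustrative OGTT.** All values are assumed. Glucose at 0/30/60/90/120 min is 108/165/185/175/160 mg/dL and insulin is 18/80/110/115/105 mU/L. Conversions: 1 mU/L = 6 pmol/L, and 18 mg/dL = 1 mmol/L.

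- ΔI = (80 − 18) × 6 = 372 pmol/L
- ΔG = (165 − 108)/18 = 3.167 mmol/L
- S = 372/3.167 = 117.5 pmol/mmol
- Mean glucose 158.6, mean insulin 85.6
- M = 10,000/√(108 × 18 × 158.6 × 85.6) = 1.95
- D = 228.7

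*Same glucose, every insulin value 10/20/30% lower:* S changes by −10/−20/−30%, M by +11/+25/+43%, and D by 0%. The zero is built in. Scaling every insulin value by a factor k multiplies S by k and M by 1/k.

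*Better glucose (98/150/160/145/130), insulin 20/30/40% lower:*

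| Insulin | S | M | D |
|---|---|---|---|
| ×0.8 | 103.0 (−12%) | 2.75 (+41%) | 283.5 (+24%) |
| ×0.7 | 90.1 (−23%) | 3.15 (+62%) | 283.5 (+24%) |
| ×0.6 | 77.3 (−34%) | 3.67 (+89%) | 283.5 (+24%) |

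Here the written index falls while the adjusted index rises. The smaller ΔG (52 against 57 mg/dL) softens the fall: 0.8 × 57/52 = 0.88 rather than 0.80. The example shows that opposite movement is possible. It does not show how likely it is.

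**The case against.** The best counter-argument is that the label is wrong but the harm is conditional. Several parts of it stand.

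- **The index need not fall.** The protocol says linagliptin works by stimulating insulin secretion and that empagliflozin may indirectly improve secretion as well as resistance. A smaller glucose rise also lifts the ratio. The constant-function table is an illustration, not a forecast.
- **Both arms receive metformin and the same lifestyle programme.** Much of any sensitivity gain is therefore common to both, and the documents do not say what the two added drugs contribute on top.
- **Matsuda is also reported.** A careful reader would see secretion and sensitivity side by side. The plan does not require them to be read together.
- **Renaming would also cure the mismatch.** Calling variable 3 early insulin secretion and reading it with Matsuda is defensible. It would leave the plan without the index it set out to use.

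A reader might infer a 29% fall in the index from the 29% reduction in insulin resistance that the background section reports for liraglutide. The documents do not support this. The same sentence reports a 21% rise in insulin secretion, and liraglutide is not a trial drug. Taken at face value, those figures give +21% on a raw secretion measure and 1.21/0.71 = 1.70, or +70%, on a secretion-times-sensitivity measure. That is understatement, not reversal. The protocol does not say how secretion was measured there, so even this mapping is loose.

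The insulin availability index and the 6-month clamp do not fill the gap. The first has no formula, and the second has no listed baseline or 12-month counterpart.

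**Conclusion.** The name and formula of variable 3 disagree, and the unit line confirms that the formula is meant as written. By identity, the written ratio understates relative sensitivity-adjusted islet function in whichever arm gains more sensitivity. With adjusted function equal, the shortfall is 9%, 17% or 23% for an assumed between-arm sensitivity advantage of 10%, 20% or 30%. The true difference between arms is unknown from the documents, so the actual size is too.

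A reader might go further and conclude that the comparison is biased against quadruple therapy. That would require evidence that this arm gains more sensitivity than metformin and lifestyle changes alone. The hypothesis expects it, but no figure in the documents establishes it. Nor is a fall in the ratio always harmless: a fall with unchanged Matsuda would suggest poorer beta-cell function.

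Should-fix. The index is not designated primary, it is one of several islet measures, and the data needed for correction are already to be collected.

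**What to change.** 1. In variable 3, define the index as [ΔI(0–30)/ΔG(0–30)] × Matsuda index, both from the same OGTT.
2. State the units of each component and of the product, and replace the unit line. The ratio is in pmol/mmol, while the Matsuda formula under Laboratory procedures and techniques uses mg/dL and mU/L.
3. If the insulin availability index listed there is meant to be the same quantity, make it refer to this definition. If not, give its formula.
4. Report the unadjusted ratio under its own name, early insulin secretion. State that it will be interpreted jointly with Matsuda, so that a fall alone is not read as loss of beta-cell function.

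The cost is a few lines of wording, fixed before analysis. The OGTT samples at baseline, 6 and 12 months already supply every input. The downside is that the product may be noisier than either component. It also shares insulin values with Matsuda, so the two are not independent pieces of evidence.

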#### 4) Pancreatic beta cell function

- a. Type of variable and level of measurement: Dependent, Quantitative of reason
- b. Indicator: pmol / mmol
- c. Conceptual definition: Pancreatic beta cell's ability to secrete enough insulin and maintain normal glucose levels
- d. Operational definition: This will be obtained using the OGTT glucose and insulin values by applying the following formula:  $(\text{IncAUCG0-120}) / (\text{IncAUCI0-120})$ , where  $(\text{IncAUCG0-120})$  = increase in the area under the curve of glucose during the 120 minutes of the OGTT obtained by the trapezoidal rule, and  $(\text{IncAUCI0-120})$  = increase of the area under the insulin curve during the 120 minutes of the OGTT obtained by the trapezoidal rule.

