### **Specific goals:**

1. Identify patients with glucose intolerance and obesity who may enter the study.
2. To assess the effect at 12 months with treatment with metformin 1700 mg / d and lifestyle modifications on insulin resistance, pancreatic islet function, and cardiovascular function in a group of patients with mixed prediabetes and obesity.
3. To assess the effect at 12 months of treatment with the combination of linagliptin 2.5 mg / metformin 850 mg every 24 h + Empagliflozin 12.5 mg / metformin 850 mg every 24 h and lifestyle changes on insulin resistance, the function of Pancreatic islet and cardiovascular function in a group of patients with mixed prediabetes and obesity.

4. Evaluate and compare cardiovascular risk markers (TNF $\alpha$ , IL6, hsPCR) before and after treatments in the 2 study groups.
5. Compare insulin resistance and pancreatic islet function between the study groups at the end of the intervention.
6. Evaluate and compare glucose metabolism using OGTT at the beginning and end of treatment in the study groups.

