### **HYPOTHESIS**

Quadruple therapy (linagliptin + empagliflozin + metformin + lifestyle modifications) has a greater effect on pancreatic islet function, insulin resistance and cardiovascular function compared to standard therapy (metformin + lifestyle modifications) in patients with mixed prediabetes and obesity.

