## **STATISTIC ANALYSIS**

The data will be presented with descriptive statistics, mean and standard or median deviation and interquartile range, as well as percentages and incidence. For comparisons of numerical variables between the study groups, we will use Student's t if the distribution of the data follows a normal pattern, otherwise the Mann-whitney U test will be used; To compare qualitative variables we will use Chi square. Delta analysis will be performed for differences between groups. It will be considered significant when the value of p is  $<0.05$ . For the analysis and presentation of the data we will use the SPSS Version 15 and GraphPad Prism 5 programs.

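### Variable 4 (beta-cell function) is written as glucose over insulin, which contradicts its own unit and the orientation of variable 3, and no direction of improvement is stated

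*Combined protocol and SAP*

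**What the plan says.** Under the heading for dependent variable 4, pancreatic beta cell function, the operational definition is "IncAUCG0-120}) / (\text{IncAUCI0-120". The two terms are then explained in words in the same order, glucose first; the denominator is the "increase of the area under the insulin curve during the 120 minutes of the OGTT obtained by the trapezoidal rule". The unit line of that variable reads "Indicator: pmol / mmol".

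Variable 3, headed "Pancreatic beta cell function (Insulin Oral Disposition Index = IDOI", has the same unit line and the same conceptual definition. Its formula is "\Delta I_{0-30}) / (\Delta G_{0-30", insulin increment over glucose increment between 0 and 30 minutes.

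Islet function is part of the hypothesis: quadruple therapy "has a greater effect on pancreatic islet function, insulin resistance and cardiovascular function". Specific goal 5 is to "Compare insulin resistance and pancreatic islet function between the study groups at the end of the intervention". The statistical section names Student's t or Mann-Whitney for numerical variables and adds that "Delta analysis will be performed for differences between groups". None of these places says whether a higher or a lower value of variable 4 counts as improvement.

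**The concern.** A formula and its unit should point the same way, and here they do not. An analyst who follows the formula gets glucose over insulin; one who follows the unit, or reads across from variable 3, gets the reciprocal. The order is repeated in the verbal definitions, so a slip in text extraction is unlikely.

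Two things are at stake. The first is interpretation: two measures of the same concept, labelled with the same unit, may be reported with opposite signs and no key to reading them. The second is the test. If the orientation is settled only after the data are seen, the choice is not always a harmless change of sign, because some of the planned tests give different p values for a ratio and for its reciprocal.

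**Working it through.** The plan gives no numerical result for variable 4, so there is no figure to reproduce. The check has three parts.

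**1. Units (from the document).**
- Variable 4 as written: (mmol/L × min) / (pmol/L × min) = mmol/pmol. Stated: pmol/mmol. They are reciprocals.
- Variable 3 as written: (pmol/L) / (mmol/L) = pmol/mmol. Stated: pmol/mmol. They agree.

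**2. Do variables 3 and 4 move oppositely? (OGTT values assumed.)** Values are at the planned 0/30/60/90/120 min, glucose in mg/dl (÷18 for mmol/L) and insulin in mU/l (×6 for pmol/L); both conversions are assumed.
- Baseline: glucose 110/175/195/180/165, insulin 15/75/100/105/95.
- A: 98/150/155/140/125, 13/85/105/90/70.
- B: 98/155/160/140/125, 9/52/65/60/45.
- C: 110/165/185/170/150, 15/80/85/75/60.

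Trapezoidal increment above time 0 = 30 × (d30 + d60 + d90 + d120/2), where d is the rise from time 0. At baseline:
- glucose: 30 × (65 + 85 + 70 + 27.5) = 7425; ÷18 = 412.5
- insulin: 30 × (60 + 85 + 90 + 40) = 8250; ×6 = 49500
- variable 4 as written: 412.5 / 49500 = 0.00833; inverted: 120.0
- variable 3: (60 × 6) / (65 / 18) = 99.7

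| Curve | Variable 3 | Variable 4 as written | Variable 4 inverted |
|---|---|---|---|
| Baseline | 99.7 | 0.00833 | 120.0 |
| A | 149.5 (+50.0%) | 0.00565 (−32.2%) | 176.9 (+47.4%) |
| B | 81.5 (−18.3%) | 0.00962 (+15.4%) | 104.0 (−13.4%) |
| C | 127.6 (+28%) | 0.00894 (+7%) | 111.9 (−7%) |

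For C: glucose 30 × (55 + 75 + 60 + 20) = 6300, ÷18 = 350; insulin 30 × (65 + 70 + 60 + 22.5) = 6525, ×6 = 39150; 39150 / 350 = 111.9. In A and B the variables move oppositely as written. In C they move together, because one covers 0–30 min and the other 0–120 min.

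**3. Does orientation change the test?**
- *Mann-Whitney, one time point, all values positive:* x → 1/x reverses the ranks, so the two-sided p is unchanged.
- *Student's t:* not invariant. With assumed insulin/glucose values 50, 100, 400 in one arm and 90, 100, 200 in the other, the means are 183.3 and 130.0. The reciprocal means are 0.0108 and 0.0087. The first arm is higher on both scales.
- *Change from baseline:* 1/x1 − 1/x0 = −(x1 − x0)/(x0·x1). Each patient's change is reweighted, so neither t nor Mann-Whitney is invariant.
- *Log change:* log(1/x1) − log(1/x0) = −(log x1 − log x0). Only the sign changes.

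Simulation of the delta analysis: log-normal ratio, 17 per arm (Sample size section), two-sided alpha 0.05. SDs and effects are assumed. Share of trials in which ratio and reciprocal give different verdicts, within-patient log SD 0.3:

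| Between-patient log SD, effect | t | Mann-Whitney |
|---|---|---|
| 0.3, ×1.3 | 20.7% | 15.8% |
| 0.3, ×1.5 | 24.0% | 19.2% |
| 0.5, ×1.3 | 27.3% | 19.3% |
| 0.5, ×1.5 | 32.5% | 22.8% |
| 0.7, ×1.3 | 30.1% | 22.8% |
| 0.7, ×1.5 | 39.7% | 26.6% |

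With smaller within-patient SD (effect ×1.5, between-patient SD 0.3–0.5):
- 0.2: 8–15% (t), 7–9% (Mann-Whitney)
- 0.15: 0.5–3.5% (t), about 0.5–1% (Mann-Whitney)
- 0.1: at most 0.1%; both orientations then reject in almost every trial

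Power at between-patient 0.5, within-patient 0.3, ×1.5, ratio against reciprocal: t 72.5% and 55.3%; Mann-Whitney 75.4% and 61.2%; t on log change 77.2%. With no true effect each version rejects in 4.1–5.2%.

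**The case against.** The contradiction itself is hard to dispute, but several limits on it stand.

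- **The unit line is not proof of intent.** Unit lines elsewhere in the section are loose: the Matsuda index is given in natural numbers, and ventricular mass and preloads sit under a percentage. The unit of variable 4 may have been copied from variable 3. Insulin over glucose is therefore the better-supported reading, not a proven one. Either way the definition needs correcting.
- **A reader might infer that the two variables will report opposite signs.** The documents do not support that: curve C shows them moving together. Opposite signs are possible, not certain.
- **A reader might infer inflated false positives.** The null simulations show none for a single test with the orientation fixed.
- **The simulation does not favour one orientation.** If treatment lowers the ratio, the power ordering reverses. What it supports is the log scale.
- **Missing direction is not peculiar to variable 4.** Glycosylated hemoglobin, the Matsuda index, the inflammation markers and the cardiac measures state none either. It matters more here because formula and unit disagree.
- **A reader might also infer that variable 3 is mislabelled as a disposition index, or that the insulin availability index in the laboratory section is a further conflicting definition.** The protocol defines neither term, so neither inference can be drawn from it.
- **The practical reach is limited.** Variable 4 is not designated primary and does not enter the sample-size formula. HOMA-B is also planned, and both orientations can be computed from the same OGTT.

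**Conclusion.** The definition of variable 4 is wrong as written: its formula yields mmol/pmol, its stated unit is pmol/mmol, and it is oriented opposite to variable 3 with no direction of improvement given. This rests on the text alone.

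The consequences are conditional. For a given glucose response, more insulin lowers variable 4 as written, so it can contradict variable 3. For positive values at one time point, a two-sided Mann-Whitney result is unaffected apart from its sign. For Student's t and the delta analysis, orientation can change the verdict: in about 0–40% of trials (t) and 0–27% (Mann-Whitney). Those ranges assume 17 per arm, between-patient log SD 0.3–0.7, within-patient log SD 0.1–0.3 and effects of 1.3- to 1.5-fold. The protocol supplies none of these SDs or effects for this ratio, so the ranges are illustrations, not predictions. What differs is power, not the false-positive rate.

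It should be corrected before analysis. It does not by itself undermine the trial's other outcomes.

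**What to change.** Before any analysis:

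1. Define variable 4 as incremental insulin area 0–120 over incremental glucose area 0–120, in pmol/mmol. This matches its stated unit and the orientation of variable 3. If glucose over insulin is truly intended, change the unit to mmol/pmol and say so.
2. State that a higher insulin/glucose ratio means more insulin secreted per unit of glucose rise, so that the reported sign can be read.
3. Analyse the change in this ratio on the log scale where values are positive, so that orientation cannot affect the test, and report how many values are non-positive.

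The cost is a few lines of text. All inputs come from the planned five-point OGTT, with no added samples or visits and no change in sample size. The one real downside is that the log scale needs a rule, written in advance, for non-positive increments.
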